The aim is to investigate the effect of sevoflurane inhalational versus propofol intravenous anaesthesia on expression of hypoxia-inducible factor 1 (HIF-1), circulating tumour cells, DNA damage and biomarkers of immunity and inflammation in patients with hepatocellular carcinoma undergoing open hepatectomy.

Aim 1: To investigate the changes in gene expression and plasma concentrations of inflammatory biomarkers (HIF-1, IL-6, and TNF-alpha) induced by surgery and the effects of different methods of anaesthesia on this expression.

Aim 2: To investigate the changes in DNA damage induced by surgery and the effects of these two different methods of anaesthesia on this damage.

Aim 3: To investigate changes in circulating tumour cells pre, intra and post-surgery

Aim 4: To follow-up patients post tumour resection for three-year survival and investigate differences in survival between the TIVA and sevoflurane cohorts.

Aim 5: To investigate the difference in post-operative pain and post-operative morphine consumption in patients anaesthetized with propofol versus sevoflurane.

Background of Research

Cancer remains a leading cause of morbidity and mortality, despite continued advances in management and treatment strategies. In 2014, 'malignant neoplasms' was the leading cause of death for both sexes in Hong Kong, accounting for 30.2% of all registered deaths [1]. Of these, liver cancer, defined as malignant neoplasm of the liver and intrahepatic ducts, has been the third leading cause of cancer death in Hong Kong for many years. In 2014, 1,585 patients died from liver cancer, accounting for 11.5% of all cancer deaths [2]. In general, the age-standardized death rate due to liver cancer was higher in males than females, with a decreasing trend in age-standardized death rates in recent years [2]. With the ageing population and the rising incidence of cancer diagnoses, anaesthesiologists are frequently managing patients with cancer in their daily practice.

[figure not shown]

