Patients will be followed up for three-year survival.

Blood-taking (*a total of 15mls on each occasion*) will take place at four time-points:

1. *Pre-operative*

This is for baseline assessment, and will be taken in the operation theatre from the IV cannula before induction of anaesthesia.

2. *Intra-operative*

This time point will be up to the discretion of the surgeon. As soon as the surgeon deems the tumour to be resected, the attending anaesthetist will take the blood sample.

3. *Immediately post-operative*

This will be taken outside the operating theatre 30 mins after arrival in the recovery room.

4. *24 hours post-surgery*

This will be taken in the general ward or intensive care unit (ICU).

Biochemical assessment of blood samples

Around 15mls of venous or arterial blood will be taken at each time point, and will be analysed for the following biomarkers:

Table 1

Biomarker	Sample	Method
Gene expression (HIF-1, IL-6, TNF-alpha)	RNA/cDNA	PCR
DNA damage (Comet Assay)	White cells	manual
hsCRP	Plasma	Commercial Kit
Glutathione Peroxidase	RBC	Commercial Kit
Superoxide dismutase	"	"
8-oxoGuo, 8-oxodG	Plasma	"
IL-6, TNF-alpha, HIF-1	plasma	ELISA
Circulating tumour cells	Whole blood	Isolation by Size of Tumour Cells

Primary outcome

The primary outcome of this study is the detection of a two-fold difference between the pre-operative blood sample and 24-hour post-operative blood sample in HIF-1 gene expression in the SEVO group, and a less than two-fold difference in the same samples of the TIVA group.

The secondary outcome is a reduction in the incidence of two-year recurrence from 40% in the SEVO group to 20% in the TIVA group.

Other secondary outcomes are listed in Table 1.

Sample size calculation

Using the primary outcome of HIF-1 gene expression of at least 2-fold difference between time points, power of 0.9 and standard deviation (SD) of 0.9, 22 patients are required in each group. To account for drop-outs, 25 patients will be recruited into each group, making a total of **50** patients.

Using the secondary outcome of two-year recurrence after hepatectomy of around 40% and an expected two-year occurrence of 20% in the TIVA group, 108 patients must be recruited into the study (total of 216 in both groups, to account for potential drop-outs **220** patients will be recruited) with an alpha of 0.05 and power of 0.9.

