For this current study preliminary analysis and publication of data will be conducted after 50 patients have been recruited. Recruitment will continue until **220** patients have completed the study.

Statistical analysis

Patient demographics, disease stage, and surgery and laboratory biomarker data will be compared between TIVA and SEVO groups using chi-square and *t* tests as appropriate. The Kaplan–Meier method will be used to calculate the overall survival of patients from the date of surgery to the date of death; patients alive will be censored at the follow-up closure date. A Cox proportional hazard regression model will be used to compare the hazard of the two groups by using a univariate model.

Impact of the study and concluding remarks

Thousands of patients with a cancer diagnosis undergo surgery in Hong Kong every year. If it can be shown that anaesthetic technique can impact survival after tumour resection surgery, then this will inform both clinicians and patients regarding the most suitable method of anaesthesia for their particular situation. Through biochemical analysis of blood samples taken pre, intra, and post-surgery, the mechanisms through which anaesthetic techniques may mitigate cancer recurrence after hepatectomy can be elucidated.

References:

1. *Leading Causes of Cancer Deaths*. Healthy HK, Department of Health 2014 [cited 2016 October 12th]; Available from: http://www.healthyhk.gov.hk/phisweb/en/healthy_facts/disease_burden/major_causes_death/cancers/cancers/.
2. Zhu, R.X., et al., *Epidemiology of Hepatocellular Carcinoma in the Asia-Pacific Region*. Gut and Liver, 2016. **10**(3): p. 332-339.
3. Abrams, P. and J.W. Marsh, *Current approach to hepatocellular carcinoma*. Surg Clin North Am, 2010. **90**(4): p. 803-16.
4. Divatia, J.V. and R. Ambulkar, *Anesthesia and cancer recurrence: What is the evidence?* Journal of Anaesthesiology, Clinical Pharmacology, 2014. **30**(2): p. 147-150.
5. Heaney, Á. and D.J. Buggy, *Can anaesthetic and analgesic techniques affect cancer recurrence or metastasis?* British Journal of Anaesthesia, 2012. **109**(suppl 1): p. i17-i28.
6. Grove, C.S. and G.S. Vassiliou, *Acute myeloid leukaemia: a paradigm for the clonal evolution of cancer?* Disease Models & Mechanisms, 2014. **7**(8): p. 941-951.
7. Vinay, D.S., et al., *Immune evasion in cancer: Mechanistic basis and therapeutic strategies*. Seminars in Cancer Biology, 2015. **35, Supplement**: p. S185-S198.

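### Biomarkers are to be compared by t tests with no covariate and no stated scale, although every patient has a pre-operative value; a prespecified log-scale ANCOVA on that value is generally more efficient and needs no extra samples.

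*Combined protocol and SAP*

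**What the plan says.** The whole biomarker analysis is one sentence under Statistical analysis: "laboratory biomarker data will be compared between TIVA and SEVO groups using chi-square and" *t* tests, as appropriate. The only models named in that section are for survival.

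Elsewhere the plan relies on a baseline:

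- Patient data collection lists the pre-operative sample first of four: "This is for baseline assessment, and will be taken in the operation theatre from the IV cannula before induction of anaesthesia". The Table 1 biomarkers are to be assayed at every time point.
- Primary outcome sets a separate criterion for each arm. The first is a "two-fold difference between the pre-operative blood sample and 24-hour post-operative blood sample in HIF-1 gene expression in the SEVO group". For the other arm, the plan expects "a less than two-fold difference in the same samples of the TIVA group".
- Sample size calculation uses "HIF-1 gene expression of at least 2-fold difference between time points, power of 0.9 and standard deviation (SD) of 0.9" to reach 22 per group, 25 with drop-outs.
- Aims 1 to 3 are worded as changes; Aim 3, for example, is "To investigate changes in circulating tumour cells pre, intra and post-surgery".
- After the sample size, the plan adds that "preliminary analysis and publication of data will be conducted after 50 patients have been recruited", with recruitment continuing to 220.

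**The concern.** The baseline is measured and is part of the question, but the analysis sentence never says how it enters. For HIF-1 the endpoint wording points to a change analysis, so a t test on log change is the natural comparator. For the other Table 1 biomarkers the plan does not say whether baseline is used at all.

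Two things are at stake. The first is precision: under randomisation, adjusting for a correlated baseline usually gives a smaller variance than either a change score or the 24-hour value alone. This matters most at the 50-patient analysis, on which the primary outcome is sized and which is to be published. The second does not depend on the correlation: with scale and baseline use both open, the form of the primary test can be settled after the data are seen.

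**Working it through.** **Inputs.** From Sample size calculation: 22 per arm, SD 0.9, power 0.9, two-fold difference. Alpha 0.05 is stated only for the recurrence calculation; two-sided 0.05 is assumed for HIF-1. The documents give neither the correlation r between pre-operative and 24-hour log values nor the ratio k of the 24-hour SD to the baseline SD. I assume r = 0.3, 0.5, 0.7, 0.8 and k = 1 or 1.25.

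**The plan's own figure.** Two-sample t test, SD 0.9, 90% power:

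| Reading of two-fold | Difference | n per arm |
|---|---|---|
| log2 | 1.00 | 19 |
| natural log | 0.69 | 37 |
| log10 | 0.30 | 189 |
| raw difference of 2 | 2.00 | 6 |

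None gives 22. Conversely, 22 per arm with SD 0.9 has 90% power for a difference of 0.90, which is neither log2(2) = 1 nor ln(2) = 0.69. Because the scale is unstated, 22 cannot be verified; this does not show it to be wrong.

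**Variance formulas**, with baseline SD as the unit:

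- 24-hour value only: k²
- log change: 1 + k² − 2rk
- ANCOVA: k²(1 − r²), times 1 + 1/(2n − 4) for estimating the slope. The factor is 1 + 1/40 = 1.025 at n = 22 and 1 + 1/212 = 1.005 at n = 108.

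Hence ANCOVA/change = k²(1 − r²)/(1 + k² − 2rk), which is (1 + r)/2 at k = 1, and ANCOVA/24-hour = 1 − r². For example, at r = 0.5 and k = 1, ANCOVA/change is 0.75 × 1.025 = 0.77, and 22/0.769 = 28.6.

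| Slope cost included, n = 22 | r = 0.3 | 0.5 | 0.7 | 0.8 |
|---|---|---|---|---|
| ANCOVA/change, k = 1 | 0.67 | 0.77 | 0.87 | 0.92 |
| n per arm the change test needs to match 22 | 33.0 | 28.6 | 25.3 | 23.8 |
| ANCOVA/change, k = 1.25 | 0.80 | 0.92 | 1.005 | 1.025 |
| ANCOVA/24-hour only | 0.93 | 0.77 | 0.52 | 0.37 |
| n per arm the 24-hour test needs to match 22 | 23.6 | 28.6 | 42.1 | 59.6 |

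**Where the gain is nil.** Against the 24-hour value: r of about 0.16 or less. Against change with k = 1: r of about 0.95 or more. Against change with k = 1.25: r between about 0.68 and 0.88, with a worst ratio of 1.025.

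Simulation (20,000 trials per setting, 22 per arm) gave ANCOVA/change ratios of 0.664, 0.766, 0.875, 0.926 at k = 1 and 0.796, 0.914, 1.004, 1.027 at k = 1.25. Type I error of each single test was 0.046 to 0.054.

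**Power at 22 per arm** for an assumed two-fold between-arm ratio, k = 1 (noncentral t; where four values are given they are for r = 0.3, 0.5, 0.7, 0.8):

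| Meaning of SD 0.9 | Log change | ANCOVA |
|---|---|---|
| SD of change, log2 | 95% | 99, 98, 97, 96% |
| SD of change, natural log | 70% | 86, 81, 76, 74% |
| SD of 24-hour value, log2 | 86, 95, 99.6, >99.9% | 96, 98, 99.9, >99.9% |
| SD of 24-hour value, natural log | 56, 70, 90, 98% | 73, 81, 93, 98% |

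The spread shows how much depends on what the plan leaves unstated; no single power figure can be claimed.

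**Two analyses.** If HIF-1 were tested at 0.05 at both 50 and 220 patients, the test statistics would correlate at √(50/220) = 0.477, giving an overall type I error of 9.1%. With 44 and 216 patients it is 9.2%.

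**The case against.** A change-score t test is valid, and for HIF-1 the endpoint already uses the baseline, so the larger gains against a 24-hour-only test do not apply to the primary outcome as worded. Against log change the gain can be small: on log2, with 0.9 as the SD of change, power rises only from 95% to between 96% and 99%. It vanishes for some correlations if SDs rise after surgery, which is plausible. At 108 per arm the log-change test has at least 99.7% power for a two-fold ratio under either reading of the SD, even on natural log, so at full recruitment ANCOVA would not alter a two-fold conclusion. The plan also allows chi-square tests, so a comparison of the proportions reaching two-fold is possible. The 9% error assumes a formal HIF-1 test at both stages, which the plan does not state.

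These points limit the weight of the concern and do not remove it. The primary outcome is sized on the 50 patients, where precision is lowest. For the other biomarkers a 24-hour-only test remains a possible reading. A possible chi-square test only widens the choice left open. Across the values in the table, ANCOVA is never more than 2.5% worse in variance than log change and is up to a third better.

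**Conclusion.** The concern holds, as a loss of efficiency and a gap in prespecification; validity of a single t test is not in question. With equal SDs and r from 0.3 to 0.8, baseline adjustment cuts the variance by 33% down to 8% against log change, and by 7% up to 63% against the 24-hour value alone. If SDs rise by a quarter after surgery, the result against log change runs from a 20% gain to a 2.5% loss. These sizes rest on assumed correlations and SD ratios that the documents do not give. The prespecification gap rests on no assumption: the scale, the quantity tested and the use of baseline are all unstated for the primary outcome. The SAP should be changed, but this is not a reason to doubt the design.

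**What to change.** 1. Prespecify the between-arm HIF-1 comparison as two-sided ANCOVA of log 24-hour expression on arm and log pre-operative expression, with the log-change t test as a sensitivity analysis.
2. State the log base, the scale of the SD of 0.9, and whether it refers to the change or to a single value.
3. State that the back-transformed arm coefficient is the between-arm ratio of fold changes. Report each arm's fold change with a 95% confidence interval beside it, because the ratio alone cannot show whether the per-arm two-fold criterion is met: a ratio of 1.7 fits 1.7 against 1.0 or 3.4 against 2.0.
4. Name either the 50-patient or the final analysis as the confirmatory HIF-1 test and label the other descriptive.
5. Use the same model for the other continuous Table 1 biomarkers, with the pre-operative value as covariate at each later sample.
6. Circulating tumour cells (method in Table 1: "Isolation by Size of Tumour Cells") can be zero. Use a count model or another prespecified transformation, adjusted for baseline.

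The cost is SAP wording and one degree of freedom, about 2.5% of variance at 22 per arm and 0.5% at 108. The pre-operative sample and its assays are already planned, so no extra blood or laboratory work is needed.

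### Aims 1 to 3 and the primary outcome concern within-patient change, but the only stated biomarker analysis is a between-arm chi-square or t test, with no paired, change-score or longitudinal analysis of the four samples

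*Combined protocol and SAP*

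**What the plan says.** **Aims and Objectives.** Aim 1 is "To investigate the changes in gene expression and plasma concentrations of inflammatory biomarkers (HIF-1, IL-6, and TNF-alpha) induced by surgery", followed by the effect of the anaesthetic method. Aim 2 has the same two parts for DNA damage: "To investigate the changes in DNA damage induced by surgery and the effects of these two different methods of anaesthesia on this damage". Aim 3 is "To investigate changes in circulating tumour cells pre, intra and post-surgery" and mentions no arm comparison.

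**Patient data collection.** Blood sampling "will take place at four time-points": before induction (described as the baseline), at tumour resection, 30 minutes after arrival in recovery, and at 24 hours.

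**Primary outcome.** This is the "detection of a two-fold difference between the pre-operative blood sample and 24-hour post-operative blood sample in HIF-1 gene expression in the SEVO group", together with "a less than two-fold difference in the same samples of the TIVA group". The remaining markers in Table 1 are secondary outcomes, with no time point or contrast named.

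**Statistical analysis.** Here "laboratory biomarker data will be compared between TIVA and SEVO groups using chi-square" and t tests, as appropriate. The other methods, Kaplan–Meier and the univariate "Cox proportional hazard regression model will be used to compare the hazard of the two groups", are for survival. No paired test, change score, baseline adjustment or repeated-measures model appears anywhere.

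**The concern.** The aims and the analysis ask different questions. A comparison of TIVA with SEVO tells us whether the arms differ. It does not tell us whether, or by how much, a marker moved during the operation. If circulating tumour cells rose sharply and equally in both arms, the planned test would correctly report no difference, and the rise that Aim 3 asks about would go unreported. Adjusting the arm comparison for baseline would not help, because the result is still an arm contrast.

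The text also does not say which of the four samples enters each t test, or whether the test uses values or changes from the pre-operative sample. That choice stays open for every marker in Table 1. The plan intends to analyse and publish after 50 patients, so the choice could be made with data in hand.

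**Working it through.** **1. Each question against the stated method**

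| Question | Quantity needed | Supplied by a between-arm chi-square or t test? |
|---|---|---|
| Aims 1 and 2, first half | Within-patient change | No |
| Aims 1 and 2, second half | Arm difference in that change | Only if the t test is run on changes, which is not stated |
| Aim 3 | Change in circulating tumour cells over the operation | No |
| Primary outcome | Pre-operative to 24-hour fold change in each arm | Quantity defined, no method given |

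**2. Why an arm contrast cannot answer the first-half questions.** Let the mean log2 change be a in SEVO and b in TIVA. A t test on changes estimates a − b. If both arms rise two-fold, a = b = 1.0 and a − b = 0.

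A paired estimate in one arm would show the rise. Assume the stated SD of 0.9 is the SD of the log2 change (the documents give neither the scale nor what the SD refers to). With 22 patients the 95% half-width is t × 0.9/√22 = 0.40, a factor of 2^0.40 = 1.32. An observed two-fold rise would then have an interval from 2/1.32 = 1.52-fold to 2 × 1.32 = 2.64-fold. With 25 patients the half-width is 0.37.

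**3. The plan's own sample size.** The inputs in Sample size calculation are a two-fold difference, SD 0.9, power 0.9 and 22 per group. On the log2 scale with two-sided alpha 0.05, n = 2 × 0.9² × (1.960 + 1.282)² / 1.0² = 17.02, so 18 per group (19 by the t distribution). The stated 22 is not reproduced. The normal formula reaches 22 with one-sided alpha 0.01, or with power 0.95. No alpha or scale is stated for this calculation, so 22 is not shown to be wrong. That is a separate matter, and the present point does not depend on it.

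**4. How much the values-or-changes choice matters.** Target: a 1.0 log2 arm difference, two-sided 0.05, power 0.9. The pre-operative to 24-hour correlation ρ is not given, so an assumed range of 0.2 to 0.8 is shown.

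*If 0.9 is the SD of the change*, the single-sample SD is 0.9/√(2(1 − ρ)):
- t test on changes: 18 per group, power 95.8% at 22 (normal approximation).
- t test on 24-hour values: SD 0.712 at ρ = 0.2 gives 11 per group; SD 1.423 at ρ = 0.8 gives 43. Power at 22 falls from 99.7% to 64.5%.
- Baseline-adjusted, SD multiplied by √(1 − ρ²): 11 to 16 per group.

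*If 0.9 is the SD of a single sample*, the change SD is 0.9 × √(2(1 − ρ)):
- t test on 24-hour values: 18 per group.
- t test on changes: 28 per group at ρ = 0.2, 7 at ρ = 0.8.
- Baseline-adjusted: 17 down to 7 per group.

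Under either reading, the unspecified choice moves the required size substantially. Baseline adjustment needs no more patients than either t test.

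**The case against.** The strongest reply is that the protocol does define a change. The primary outcome is a pre-operative to 24-hour difference within each arm, the sample size rests on a difference between samples in time, and the first sample is called a baseline. A between-arm t test on change from that baseline is therefore a natural reading. It would answer the second half of Aims 1 and 2, and arm mean changes would probably be tabulated with it. Simple paired tests would then complete the aims, so a mixed model is partly a preference.

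Much of this stands, and it rules out several stronger readings that a reader might draw:

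- *That change is never estimated.* The primary outcome defines a change for one Aim 1 marker and one pair of samples. What is missing is a method for it.
- *That the serial samples are treated as separate cross-sections.* The text does not say whether values or changes are tested. Unspecified is as far as it goes.
- *That an unpaired test would be applied to pre- versus post-operative values, giving wrong standard errors.* The stated comparison is between arms, so the plan does not propose this.
- *That 12% of 24-hour samples will be missed.* The 3 in 25 is a general drop-out allowance. The 220-patient calculation allows only 4 in 220, or 1.8%.
- *That the gain from pooling both arms measures the cost of the plan.* It compares two paired analyses, neither of which the plan states.

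The reply does not supply a stated analysis for Aim 3, for the first half of Aims 1 and 2, or for the arm-specific changes in the primary outcome. It also leaves the intra-operative and recovery samples without any named use.

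**Conclusion.** The point holds as a mismatch between questions and methods. Followed as written, the plan has no analysis for Aim 3 or for the first half of Aims 1 and 2. Its primary outcome is a change for which no test or estimate is specified, and the input to the biomarker t tests is left open. This conclusion rests on the text alone. The figures illustrate what the open choice can cost, and they depend on the log2 scale, two-sided alpha 0.05, the reading of the SD of 0.9 and the assumed correlations.

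One limit applies to any repair. Every patient has both surgery and a general anaesthetic, and there is no non-surgical control. A within-patient change is therefore perioperative change under surgery and anaesthesia together. A reader might take it as the effect of surgery alone, and the design cannot support that.

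The gap is in the analysis text and not in the data, since all four samples are already planned. It should be closed before the 50-patient analysis.

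**What to change.** For each continuous marker, replace the t test with one repeated-measures mixed model on the log scale: time with four levels, arm-by-time, a common pre-operative mean (the first sample precedes induction, so randomisation supports this) and an unstructured within-patient covariance. Include every patient with at least one sample.

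Report, in this order:
1. The change from the pre-operative sample at each later time, by arm (the primary outcome's own quantity) and pooled, labelled as perioperative change under surgery and anaesthesia together.
2. The arm difference in change at each time, with the pre-operative to 24-hour HIF-1 gene expression contrast named as primary.

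For circulating tumour cells, use a repeated-measures count model of the same structure. If it is fitted by GEE, apply a small-sample correction at the 50-patient analysis. A count mixed model is an alternative that handles missing samples under weaker assumptions.

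The cost is SAP wording and some programming. No new samples are needed.
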